Total purchasing sites with a special interest in mental health problems are being identified during an initial series of visits to all sites which are due to be complete by the end of 1996. GPMH sites have, by definition an interest in mental health problems. By a combination of telephone interview and site visits, standard fundholding practices will be identified which can act as reference practices for the TP and GPMH sites. The aims of individual sites will be established by a combination of information from their purchasing plans, and interviews with lead GPs and fund managers.

Accessibility of services

Information about availability of services will be obtained partly at the initial interview at every Total Purchasing site. Sufficient information will be needed at this interview to characterise current service provision for sites with a mental health interest to identify reference practices. This basic information on availability of services will need to be supplemented during telephone interviews in early 1996. Subsequent data on availability will be collected by questionnaire or

telephone interview focused on mental health problems with the Total Purchasing manager at every site in late 1996 or early 1997. Information will also be collected from key stakeholders and providers in GPMH sites in the first part of 1996, and subsequently, depending on when they have 'live' budgets.

The composite information collected from questionnaires and telephone interviews will cover details of provider contracts (which may tend to focus on more severely mentally ill people) and of services bought in to the site (which may tend to focus on more minor mental illnesses) and also the site's strategic aims and intentions for developments, including the Care Programme Approach. (The functioning of the CPA may be able to be assessed by asking sites specifically to collect data on the number of CPA meetings attended by GPs, this information being sought from practices or provider groups.) This part of the study will address all mental health services, not just those related to severely mentally ill people.

Information on availability of services will be collected from all Total Purchasing sites, allowing comparison between Total Purchasing sites with and without a special interest in mental health (see appendix). Contracts will be reviewed to assess what are the aims for the quality and provision of services, and also the criteria for assessing quality.

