A different perspective on the availability of services will also be sought from all the Provider units related to a sample of the Total Purchasing sites with and without a special interest in mental health and from GPMH sites. By means of telephone interviews with Clinical Directors followed where necessary by personal visits, the relative contributions of the different purchasing models to changes in the availability and configuration of services will be defined, comparing the start-up period with one year later.

Utilisation of services

Information about *utilisation* of services will be obtained from hospital in-patient episode databases, focusing on admission rates and length of stay for patients with diagnoses in ICD9 Chapter V who are registered with GPs in each Total Purchasing site, in GPMH practices, and also in each reference site. These data will be analysed for April 1995 to March 1996, and for April 1996 to March 1997. Information will be sought from the study sites about any action taken to reduce admissions and length of stay, e.g. the employment of nurses to visit the in-patient units to expedite discharge.

For out-patient referrals information will be sought from the relevant providers including practices and Community Mental Health Teams by means of available databases (including practice billing systems) and also through individual Community Psychiatric Nurse workload schedules in the sample of Total Purchasing, GPMH and reference sites selected for special study. This will depend on the availability of routine nursing data being available from existing sources. Reliable

outpatient information will be difficult to collect because of the wide variety of types of secondary mental health contact, and it will not be possible to determine how much out patient data will be collected until individual sites are visited. Changes in outpatient utilisation rates are not essential to this part of the study.

Needs assessment and information systems

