Information about need assessment and information systems including the use of registers will be sought by telephone interview or questionnaires to the relevant managers of each Total Purchasing, GPMH and reference site included in the sample for special study. This will be supplemented by telephone interviews both with the relevant managers of the providers used by the special study sites and also with representatives of the relevant Health Authorities or Commissions (the first contact being aimed at a Consultant in Public Health Medicine).

Relationships with Health Commissions and Local Authorities

Information about relationships with authorities will be obtained during the same telephone interviews of the relevant managers of each Total Purchasing, GPMH and reference site included in the sample for special study and with representatives of the relevant Health Authorities or Commissions (probably Consultants in Public Health Medicine). It will be supplemented by telephone interviews with representatives of the relevant Local Authorities and Housing Departments if information about those areas is not obtained via the Health Authorities.

The data collection exercise for Total Purchasing sites, GPMH sites and reference sites will be repeated after 12 months of operation of the schemes, allowing for identification of changes before and after the sites had budgets which included the full range of mental health services.

Sample size and power

In relation to strategic aims and configuration of services, data will be collected from all the TP and GPMH sites. For admission rates, data will be collected and analysed from routine data available at the National Casemix Office in Winchester. The sample size of both groups is fixed and any modest increase of statistical power from choosing more than one reference site for each TP or GPM site would add relatively little to the study. Power calculations were done on recent data from 2 East Anglian counties which had mean (geometrical mean) psychiatric admission rates of 0.8 and 0.4 admissions per 1000 patients per year. The study would have the power to detect a reduction in rates in TP sites to 0.55 and 0.3 respectively, i.e. a reduction in admission rate of between a quarter and a third (80% power, 5% significance). The power to detect changes in admission rates in GPMH sites will be less than this because of their reduced numbers.

Assessment instruments

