The field work would begin in January 1996, related to the lead-in period for Total Purchasing, for visiting GPMH practices and establishing a baseline for Total Purchasing and reference sites. Visits to the providers on the one hand, and to stakeholder groups on the other, would be spread evenly over the 18 months after April 1996, giving a 12 month follow-up for the various sites which would be entered into the study in a staggered manner. Time for analysis would also be allowed within the on-going survey work. The final writing up would occupy the last 3 months of the 2 year study.

Identical methods would be used to study standard fundholding which was extending to include mental illness in-patient treatment. Therefore there would be economies of scale and the time frame would also be identical.

The present funding proposal is for two years. The power of the study to detect differences between the purchasing models will be considerably enhanced if funding becomes available for an additional year, as this will give more time for service reconfiguration to take place.

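### GPMH admission rates are split at 1 April 1996, although the plan leaves open when those practices' budgets go live

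*Protocol*

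**What the plan says.** In the mental health proposal, Study 1, under Utilisation of services, admission rates and length of stay are taken from hospital inpatient databases for patients "who are registered with GPs in each Total Purchasing site, in GPMH practices, and also in each reference site". The periods are then fixed for all three groups: "These data will be analysed for April 1995 to March 1996, and for April 1996 to March 1997".

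Other parts of the proposal tie timing to the schemes themselves:

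- Under Accessibility of services, information is to be collected "in GPMH sites in the first part of 1996, and subsequently, depending on when they have 'live' budgets".
- At the end of Relationships with Health Commissions and Local Authorities, the data collection exercise "will be repeated after 12 months of operation of the schemes". The stated aim is to see changes before and after sites held budgets covering the full range of mental health services.
- Under Funding for the Group of Four Linked Studies, visits to providers and stakeholder groups are spread over 18 months from April 1996, "giving a 12 month follow-up for the various sites which would be entered into the study in a staggered manner". The next paragraph says of the fundholding extension: "Therefore there would be economies of scale and the time frame would also be identical".

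Under Sample size and power, the baseline is "mean (geometrical mean) psychiatric admission rates of 0.8 and 0.4 admissions per 1000 patients per year". The detectable change is given for TP only: "The study would have the power to detect a reduction in rates in TP sites to 0.55 and 0.3 respectively". GPMH power is said to be lower, and the only reason given is the smaller number of sites.

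**The concern.** A before-and-after estimate needs the cut between the two periods to fall where exposure begins. For admission rates the cut is a calendar date common to every group. For the rest of Study 1 it is the point at which a site holds its budget. Nothing in the proposal reconciles the two. It does not state GPMH live dates, set aside months without a live budget, or treat exposure as varying over the year.

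Any month of 1996/97 before go-live is therefore counted as GPMH purchasing when it was not. Any month of 1995/96 after go-live is counted as baseline when it was not. Both errors pull the GPMH effect towards zero. Admission rate is the only Study 1 outcome with a stated power calculation, so a small observed change there would be read as evidence about the purchasing model.

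**Working it through.** **The plan's own figures.** From the rates under Sample size and power, 1 − 0.55/0.8 = 31.25% and 1 − 0.3/0.4 = 25%, which agrees with the plan's statement of a quarter to a third. The 80% power cannot be reproduced, because no standard deviation, number of units or person-years is given. These effect sizes are stated for TP. They are used below only to illustrate.

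**Late start.** Let R be the rate without GPMH purchasing, d the proportional reduction once live, and m the months of April 1996 to March 1997 before go-live. Assume no effect before go-live and the full effect from then on.

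After-year rate = R[m + (12 − m)(1 − d)]/12 = R[1 − d(12 − m)/12]

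The observed fall is d(12 − m)/12. The values of m are assumptions.

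| m | Share of effect kept | 0.8 falls to (true 0.55) | Observed fall | 0.4 falls to (true 0.30) | Observed fall |
|---|---|---|---|---|---|
| 0 | 100% | 0.550 | 31.25% | 0.300 | 25.0% |
| 3 | 75% | 0.613 | 23.4% | 0.325 | 18.8% |
| 6 | 50% | 0.675 | 15.6% | 0.350 | 12.5% |
| 9 | 25% | 0.738 | 7.8% | 0.375 | 6.3% |

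**Effect on power.** Suppose a comparison had 80% power, two-sided 5%, for the undiluted effect. Power becomes Φ(k(1.96 + 0.84) − 1.96), where k is the log of the diluted rate ratio divided by the log of the true one. At m = 3, k is 0.71 to 0.72 and power is about 52%. At m = 6, k is 0.45 to 0.46 and power is about 25%. GPMH starts from an unstated lower figure.

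**Early start.** If go-live is p months before 1 April 1996, the baseline-year rate is R(1 − dp/12) and the after-year rate is R(1 − d). The absolute difference is Rd(12 − p)/12, so the same share is lost. With R = 0.4, d = 0.25 and p = 3, the baseline is 0.375 and the after rate 0.300: a difference of 0.075 instead of 0.10.

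**Does realignment pay for its lost months?** With Poisson variation only, using 12 − m months in each year multiplies the standard error by about √(12/(12 − m)): 1.15 at m = 3 and 1.41 at m = 6. The aligned signal-to-noise ratio is then 1/1.15 = 0.87 and 1/1.41 = 0.71 of the ideal. The fixed window gives about k, that is 0.71 to 0.72 and 0.45 to 0.46. Aligning is better even after the loss of data.

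**TP sites.** Section 3 (The Intervention and its Context) says some sites will start purchasing gradually during 1995-96. Section 4 (Method) says a few may offer nearly two years of commissioning. Those sites have exposed months in their own baseline year, by the early-start formula.

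**The case against.** The strongest reply is that there may be no misalignment. The wording about live budgets fits a single common date not yet known when the proposal was written. The proposal says the GPMH time frame is identical to that for TP, and Section 2 says the great majority of TP sites begin purchasing in April 1996. The maternity proposal has its own fundholding pilot buying from April 1996. If GPMH does the same, the loss is zero. This stands: the documents do not show that live dates differ or fall late. A reader might infer staggered budgets from the passage on staggered entry, but its subject is study visits to providers and stakeholder groups.

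A second reply is that financial years suit routine data and keep seasons and reference practices aligned, and that naming two data years does not bar analysis by month within them. That is a good reason to keep the yearly tables. It does not justify resting the effect estimate on a cut that may not be the start of exposure.

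Third, the step effect is a simplification. Section 3 expects most contracts to be largely unchanged in the first year, and Section 4 anticipates changes made in prospect of TP. The fractions are therefore illustrations, not predictions.

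A reader might also infer that the fixed year favours TP over GPMH because TP begins on 1 April. The documents do not support that. Some TP sites start earlier, which dilutes their own contrast, and Annexe 1 (question E3) allows TP sites to leave services with the health authority. The net direction cannot be determined.

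**Conclusion.** The concern holds as a conditional one. The plan fixes the calendar split for GPMH practices while leaving their start of exposure open and defining change elsewhere by when budgets were held. Any departure of the live date from 1 April 1996, in either direction, biases the GPMH before-and-after estimate towards no effect. On the absolute scale the loss is one twelfth of the effect per month, under a step effect at go-live. The delay is not given, so the actual loss is unknown and may be nil. A reader might conclude that a false negative for GPMH is likely. That would need live dates and a GPMH effect size, and the documents give neither. The bias in TP versus GPMH has no known direction. The change is worth making because it is cheap and protects the one Study 1 outcome with a power statement.

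**What to change.** 1. Record each GPMH practice's live-budget date and each TP site's actual start of mental health purchasing. The proposal does not say these dates are being collected, so add the question to the planned interviews.
2. Keep the two financial-year tables as description.
3. Base the before-and-after estimate on live months up to 31 March 1997 against the same calendar months of the earlier year. Put the matched reference practice on the same months and use person-months (list size × months) as the denominator. For a start during 1995/96, use only the calendar months that precede go-live in that year and their counterparts in 1996/97, so that no month is exposed in both years.
4. Show months of 1996/97 before go-live separately as a preparatory period.
5. Reconcile the fixed years under Utilisation of services with the live-budget wording under Accessibility of services, the budget-based before and after in the closing paragraph on data collection, and the identical time frame stated under Funding. Under Sample size and power, name shorter exposed time as a further possible reason for lower GPMH power.

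The cost is a change of analysis wording, one added question, and a routine data request that includes admission dates. The downside is fewer exposed months and wider intervals for late starters. If all GPMH budgets go live on 1 April 1996, the GPMH results are unchanged.

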Appendix

Design issues in the evaluation of purchasing models: specific issues from the overall evaluation of Total Purchasing (TP) relevant to the mental health extension of standard fundholding (GHMH)

Two important design issues need to be considered in the evaluation of Total Purchasing. The first relates to the comparisons to be made and the choice of total purchasing sites for these comparisons, and the second relates to the choice of reference practices. These issues are relevant to all parts of the total purchasing project where we intend to study a small group of practices (eg mental health, maternity, A&E, community care, prescribing, transaction costs), but also to analyses which will involve all total purchasing practices. These issues are relevant to the research questions which are being addressed in the evaluation of GPMH practices.

1. Choice of comparisons to be made

1.1 Parts of the study where data are available for all practices

For some aspects of the study, we will be looking at all total purchasing sites and GPMH sites. These include the nature of services being purchased, relationships with health commissions etc. In these parts of the study, the unit of both data collection and analysis will be the site rather than the individual practice, although there will be limited opportunity to examine variation within sites. In relation to services purchased, comparisons in these areas will be able to be drawn between what the TP sites are doing, and what their host health commissions are doing for on behalf of the patients of non TP practices.

For the routine data on referrals, admissions and length of stay, the unit of analysis will be the individual practice. Certainly no attempt should be made to analyse by individual referring GP because these data are unreliable. Because data are available by practice, we will have the opportunity to analyse differences within sites and between sites as well as differences between TP sites GPMH and reference practices (see below). We should make use of this opportunity, since within site variation may be large. We will also have the opportunity to look specifically at individual groups, eg. Sites which have a specific interest in mental health. The appropriate comparisons will then be of rates within sites with a special interest, between special interest TP sites and TP sites without a special interest, and between TP sites GPMH and reference practices. We may also have the opportunity to examine differences between large and small sites, and differences between sites where a wide range of services is being purchased contrasted with those where purchasing responsibility is only being taken on for a narrow range of services.

1.2 Parts of the study where data will be collected from selected practices.

For the study of TP sites with a special interest in mental health services and GPMH practices, we will be selecting a small number of sites for more detailed study, and in each case we are likely to have to focus on one or two practices within any one site. In each case, our resources will only allow us to study a relatively small number of practices, probably ranging from 3 to 10. There is then a question of whether the TP practices selected for special study should be randomly selected or selected from among those with a special interest in a particular field. A working definition of a site with a special interest is that it should have an expressed intention in the business plan to reconfigure services in that area, or an informally expressed interest which is matched by identifiable commissioning initiatives.

It would be possible to compare randomly selected total purchasing practices with reference practices to identify the overall effect of total purchasing on one particular service. These could also be compared with GPMH practices. However, this would risk missing important effects, especially as our study is confined to the first year of total purchasing, and sites are only going to have the time and energy to address a few issues within their purchasing strategy - the rest of the contracts are likely to be largely unaltered in the first year. Because of the short term nature of the study, it would be preferable to seek maximal effects rather than average effects across the whole group of total purchasers.

The alternative is to focus specifically on practices which have a special interest in a particular area. If practices selected for study are those with a expressed special interest (eg. in mental health problems), and these are compared to reference practices who are neither total purchasers, nor have a special interest in mental health, then we are measuring the combined effect of being a total purchaser and wishing to produce change in mental health services. The results of our analyses will be criticised on the grounds that we are unable to distinguish between these two possible drivers of change. The analyses would answer the question 'What could be achieved by a practice that both has an interest in mental health and is a total purchaser?'. Likewise, study of GPMH practices will also address this question since these practice have specifically applied for a mental health extension to standard fundholding. The effects seen are likely to represent the maximal effects that could be achieved within the parameters which we are examining. This is a valid approach, but we need to acknowledge that the effect of both purchasing model and special interest in mental health is being measured.

Isolation of the special interest effect might be achieved by comparing TP practices with a special interest with non TP practices who also have the same special interest. However, it is likely to be very difficult to identify reference practices which have explicit objectives to change the services in a particular area - so comparison with non-TP special interest practices is unlikely to be feasible. Furthermore, an attempt to identify local non TP practices which share a common special interest with the TP practices implies that 'special interest' and 'total

purchasing' are independent variables: this is not the case as some practices may have gone into total purchasing precisely because they wish to produce change, and furthermore, these changes may impact on the District as a whole, the 'Vanguard' effect. For this reason, it would be desirable in some cases to compare TP sites with practices in districts which do not have TP sites.

It will be possible to examine the effect of special interest within total purchasing sites. Comparisons could be made between total purchasing practices with a special interest (eg. in mental health) with those who do not have not expressed a special interest. This would isolate the special interest effect from the total purchasing effect, and would be the most efficient way to disentangle the special interest effect from the total purchasing effect.

Where resources permit, the following comparisons should be considered:

- I. All total purchasing practices versus all other practices in the district
- ii. Total purchasing sites with a special interest in a particular area, and GPMH practices, against selected reference practices
- iii. Total purchasing practices with a special interest against total purchasing practices without an expressed special interest in that area.
- iv. Total purchasing practices with a special interest against reference practices in districts without any TP sites

In practice, it is likely to be neither feasible nor desirable to collect data for all four comparisons for each of the subjects to be studied. The following matrix suggests which comparisons might be feasible. It relates specifically to the Total Purchasing evaluation.

In each case, what is actually done will be dependent on the resources available. Within any individual column, comparisons in the rows nearer the top of the table will in general take priority over comparisons in rows lower down.

This table also puts the mental health evaluation in the context of other parts of the total purchasing project.

	Range of services provided	Routine activity data	Service efficiency	Trans- action costs	Mental health	Comm- unity care	Maternity services	Presenting	A&E
All TP practices : GPMH practices versus all local non TP GPMH practices, he rest of district	*	*	*	×	Data in previous columns only	-	_	×	?
Special interest TP practices / GPMH versus selected local reference practices	-	-	-	-	*	*	*	-	*
Special interest TP practices versus non special interest TP practices	*	*	-	-	*	×	*	-	×
Special interest TP practices vs health districts without TP	?	*	?	*	-	·?	?	*	_

Table 1. Possible comparisons to be drawn in each of the major study areas

Although comparisons marked with a question mark on the bottom line look difficult to make, there may be opportunities to choose research instruments to facilitate comparisons with other widely based studies, eg. The audit commission survey of maternity services, PSSRU survey of community care, National Primary Care Centre's work on 24 hour emergency centres.

2. Choice of reference practices.

In parts of the study where a small number of practices will be selected for more detailed study, greater attention needs to be given to identification of reference practices. In general, reference practices should be chosen form the same region, and they will often be from the same district. In each case, important factors to be controlled for should be considered under the main headings of:

Nature of provider market

[figure not shown]
Characteristics of practice / population

Some of the factors to selected under each of these headings are suggested in table 2. In each case, our ability to control for more than three or four characteristics may be severely limited. For a number of studies, ie mental health, community care, A&E and maternity, the major change being examined is an alteration of the configuration of services from secondary care or social services providers. It is therefore important that the reference practices should be chosen who use the same provider, eg mental health services, maternity hospital, social services department etc. A second important factor to consider may be rurality, as within one district, urban practices may have very different access to services compared with rural practices. A third factor is the social class mix of the practice population. This may be important if total purchasers start to purchase some types of care from the private sector, and is highly likely to be related to use of social services and A&E.

	Mental health	Community care	Maternity services	A&E	
Provider Existence of community mental health team, or psychiatnst as mai route of referral		Pre-existing high/low residential care provision	Single large maternity hospital / existence of local GP delivery facilities / type of midwifery care	Community hospital / other minor injury provision	
Practice/ population	Social class Rurality	Social class Age structure of population	Social class Rurality Age structure of population	Social class Rurality	

[figure not shown]
Table 2. Factors to be controlled for in selection of reference practices

These notes are have contributed to the development of the evaluation protocol on the impact of purchasing models on mental health services. They are included to indicate the issues which have been considered in deciding how most effectively to mount the evaluation described n the accompanying proposal.

NATIONAL EVALUATION OF TOTAL PURCHASING PILOT SCHEMES 1995-1997

SERVICE PROVISION, OUTCOMES AND COSTS FOR PEOPLE WITH COMPLEX NEEDS FOR COMMUNITY AND CONTINUING CARE

TOTAL PURCHASING EVALUATION TRACER STUDY

SERVICE PROVISION, OUTCOMES AND COSTS FOR PEOPLE WITH COMPLEX NEEDS FOR COMMUNITY AND CONTINUING CARE

January 1996

Lead:

[name], NPCR&DC at Salford

Research team:

[name], [name], NPCR&DC (Salford & Manchester). [name]. Sefton HA, [name], Kings Fund Policy Institute & LSE

(Cost/benefit study).

INTRODUCTION

The aim of this proposal is to evaluate the extent to which TPP sites can deliver demonstrable improvements in the planning and provision of community and continuing care services for elderly people with complex needs. 'Complex needs in this context are defined as the needs of those people who are assessed as eligible for packages of health and social care with the aim of enabling them to live 'independently' in their own homes. This will include a focus on the provision of NHS continuing care within this context. The study will compare the performance of Total Purchasing Pilot (TPP) sites with HA responsibility for Community and continuing Care in the context of Standard Fundholding (SFH) sites

The study has a focus on. (i) strategic developments; (ii) organisational arrangements. (iii) contracting activity. (iv) service delivery; and (v) the costs and benefits of services. The study is divided into three stages. Stage 1, identifying planned activity in relation to community & continuing care on TPP sites, is underway at present. Stage two has a primary focus on strategic development, organisational arrangement, contracting and patterns of service delivery in relation to community and continuing care on a sub-sample of TPP sites. During this stage, which would take place between April 1996 and March 1997, patients and carers experience will be explored using qualitative methods. A third stage involving a more formal cost benefit analysis is also proposed for 12 morahs beginning in April 1997.

This design has been strongly influenced by constraints on time and resources. The proposed work with patients and carers during the second stage would provide important qualitative insights in their experiences. However, without the third stage, the proposed evaluation would not provide any quantitative information on the costs and benefits of TPP in the areas of community and continuing care. The cost-benefit analysis proposed in the third stage of this study would also be limited. To obtain the detailed information on health status impact required for a full-scale cost-benefit study would require a complex and extensive study design with considerable resource implications. However, the modest proposal outlined here would provide an important indication of any relative gain achieved by TPP sites over SFH/HA purchasing of community and continuing care

BACKGROUND

The NHS and Community Care Act (1990) introduced a new system for the planning and provision of community care. It made local authorities responsible for co-ordinating community care provision to enable people affected by ageing or disability to live as independently as possible. The Act placed primary responsibility for planning, much of the provision and, therefore the funding, with local authorities. However, the legislation also specified that at both strategic and operational levels local authorities should work closely with health authorities.

Since the introduction of the legislation, health authorities have been involved with local authorities in a wide range of strategic work on community care. This has included the production of annual community care plans, market management and financial planning as well as policy development in relation to particular population groups. Operationally, health authorities have also worked with local authorities on a wide range of issues including the development of the assessment process and monitoring and improving discharge procedures, as well as jointly commissioning specific services. Whilst it is not possible to give figures, it would appear that health authorities are allocating proportions of their HCHS resources to community care beyond those traditionally allocated to community health services. In partnership with local authorities, health authorities are also gaining access to a wide range of non-mainstream sources of funding to support developments in community care provision.

Primary and community health services (including but not restricted to community nursing) make an important contribution to community care beyond the direct provision of services. In particular, they act as gatekeepers to the community care assessment process, as advocates for patients within this process and they are variously involved in the assessment process itself.

The NHS is also involved in the commissioning and provision of long term care for some groups of patients, clearly an area with close links to community care. NHS continuing care has been the focus of considerable discussion since the 1990 Act was implemented, and as long stay beds have been closed. The recently published guidance on NHS continuing care (Circular HSG(95)) is aimed at clarifying areas of responsibilities between the NHS and local authorities. Health authorities have been charged with establishing and agreeing eligibility criteria for NHS continuing care with local authority and GP involvement by April 1996.

TOTAL PURCHASING AND COMMUNITY CARE

Given this background, it is clear that Total Purchasing could involve greater powers and responsibilities for the commissioning of community care services than are made available to SFH. Within the overall framework of the joint commissioning arrangements between the health authority and the local authority, TPP sites can assume a significant role in the planning and purchasing of community care for their patients. TPP sites will also have new responsibilities for long stay/continuing care provision. Although this has to date been viewed in terms of the provision of NHS hospital beds, discussions about this area - particularly following the continuing care circular - are increasingly recognising that much continuing care may be appropriately provided outside hospitals within residential/nursing homes and within a domiciliary context.

Not all of the TPP sites will chose to focus attention on the community/continuing care area in the first year However, there are some sites which have expressed an intention to give priority to work on services for frail elderly people and/or work with local authority social services. Detailed study of a sample of these sites will allow the evaluation team to consider the potential of TP to improve the cost-effectiveness and appropriateness of the NHS contribution to community and continuing care services.

It is also important to note that there are other (non TP) models of commissioning throughout the UK (e.g. Locality Commissioning) through which primary care providers are actively involved in the commissioning of community care. These parallel developments provide an important context for the work described here. Many of the problems associated with the engagement of general practice with community care are not necessarily related to whether or not a practice is a fundholder. The NPCR&D Centre is presently considering what work it will undertake in relation to these alternative models of commissioning and the study proposed here would be conducted in close association with any related research at the National Centre and opportunities for comparative work would be explored.

It is not possible at this stage to describe in detail the range of potential TPP initiatives in the area of community/continuing care. There may well be incentives for TPP sites to get patients out of hospitals or to avert admissions by investing in domiciliary support to maintain people in the community. TPP sites may also be prepared to make greater use of private and voluntary sector services. There is also the possibility that TPP sites will attempt to shift costs onto the local authority, making their involvement in the discussions on the criteria for NHS continuing care and their implementation very important. At present HA are consulting on their guidelines/criteria for providing continuing NHS care. It will be important to explore the nature and extent of TPP sites involvement in this process and the subsequent implementation and operation of agreed guidelines

Whilst the analysis of routine activity data at all TPP sites (see section 5.2, of main evaluation proposal.) will enable some monitoring of the use of long term care by TPP sites compared to other purchasers, many of the potential changes in care options will not be captured fully by routine systems and will require data collection at the site or practice level. A further reason for detailed research on community and continuing care in a small number of TP sites is the fact that the choices made by TP sites are likely to be sensitive to the relative costs of care packages. In the case of elderly people with complex health and social care needs, community domiciliary care can often be more costly than nursing or residential care with hospital care more costly still. However, there are substantial local variations in these relative costs which are best explored in detailed case-study work.

OBJECTIVES

The objectives of this part of the nation-wide consortium evaluation of TPP is to compare strategic and operational developments around community and continuing care and to consider patient and carers experience at a sample of TPP sites with the situation in SFH sites in the Health Authorities within which the TPP sites are based. The comparison would be in five key areas.

- (i) the nature and extent of involvement in strategic development of policy in relation to community and continuing care policy;
- (ii) organisational developments to plan, manage and deliver continuing/community care.
- (iii) commissioning activities (including contracting) in relation to continuing/community care.
- (iv) patients' and carers' experience of and satisfaction with the services received; and
- (v) the cost-effectiveness of packages of care.

